1.1 Background

Facioscapulohumeral muscular dystrophy (FSHD) is a rare disabling disease with an estimated worldwide population prevalence of between 1:15,000 and 1:20,000 ([Statland and Tawil, 2014](#)), or approximately 16,000 to 21,000 affected individuals in the United States. A higher prevalence rate of 12/100,000 was reported in a population-based study in the Netherlands ([Deenen et al, 2014](#)). About two-thirds of cases are familial-inherited in an autosomal dominant fashion, and one-third are sporadic. FSHD is characterized by descending progressive skeletal muscle weakness affecting the face, shoulders, arms, and trunk, followed by weakness of the distal lower extremities and pelvic girdle. Symptoms typically first appear later in the second decade of life but can begin at any age ([Tawil et al, 2015](#)). Most cases present with shoulder girdle weakness, which is eventually found in nearly all patients ([Padberg, 1982](#)). Muscle biopsies show myopathic or dystrophic changes, including variability in fiber size, rounded fibers, central nuclei, necrotic or regenerating fibers, increased connective tissue, and fatty deposition. Up to one-third of muscle biopsies show a lymphocyte-predominant perivascular inflammatory infiltrate ([Statland et al, 2015b](#)). Muscle strength, as measured by quantitative muscle testing, decreases at an average rate of 1% to 4% per year ([Statland and Tawil, 2014](#)). The most frequent newly developed functional motor limitations include difficulty getting up from lying down in bed and difficulty using arms for activities of daily living ([Statland and Tawil, 2014](#)). The 6-year risk of wheelchair use is 24% ([Statland et al, 2015a](#)). All quality of life domains on the 36-Item Short Form Health Survey are significantly impaired, and over half of patients with FSHD report at least mild to moderate pain ([Moris et al, 2018; Padua et al, 2009](#)). Asymmetry of muscle involvement is common. Cardiac muscle is spared, and respiratory muscles are involved in a minority of patients.

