8.3. MSK MRI Muscle Fat Fraction, Lean Muscle Volume and Muscle Fat Infiltration

Measurement of the extent of skeletal muscle tissue replacement by fat in FSHD patients will be done through automatic skeletal muscle segmentation for the 3D muscle volumes and fat fraction analysis via robust algorithms using Dixon imaging. This will be assessed at Screening, Week 12, and Week 48.

A. Composite measures: Composite variables, incorporating pre-selected muscles, will be derived for longitudinal analysis of muscle fat fraction, lean muscle volume and muscle fat infiltration (MFF_{tot} , LMV_{tot} , and MFI_{tot} respectively), as described in [Appendix 15.6](#). The scores will be derived by scientists at the MRI Service Provider (AMRA Medical Inc.) in a blinded fashion, with no access to treatment assignment information.

For each treatment, descriptive statistics of MFF_{tot} , LMV_{tot} , and MFI_{tot} per visit as well as changes from baseline will be presented. A Mixed Effect Model for Repeated Measures (MMRM) model will be used to analyze the change from baseline in each composite MRI score, with repeat number category, treatment group, visit, and treatment-by-visit interactions as fixed effects and baseline value of the parameter as a covariate. Within-group LS mean changes from baseline, the associated SEs and 2-sided 95% CIs, treatment differences in LS mean changes from baseline at Weeks 12 and 48 and the associated 2-sided 95% CIs and 2-sided p-values will be derived from the MMRM model and will be provided in the summary table. An unstructured covariance matrix will be used to model the correlation among repeated measurements within each subject. If models using unstructured covariance do not converge, an AR(1) covariance structured will be used instead. **LMV_{tot} is the key endpoint for hypothesis testing.**

B. Individual Muscles: For each muscle location, a similar method will be used to analyze muscle fat fraction (%), lean muscle volume (L), and muscle fat infiltration (%) per visit as well as changes from baseline.

The LS mean change from baseline by visit of the MSK MRI muscle fat fraction, lean muscle volume, and muscle fat infiltration will be graphically presented.

The change from baseline in the composite parameters will also be summarized by subgroups identified in [Section 4.6](#) to evaluate consistency of treatment effects across the subgroups.

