8.4. Clinical Outcome Assessments

8.4.1. Reachable Work Space With and Without Weights

The reachable work space (RWS) is a 3-dimensional sensor-based system (using a single depth-ranging sensor) that can unobtrusively detect an individual's RWS and reflects an individual global upper extremity function, including shoulder and proximal arm. The evaluation will be performed with and without weights and on both the right and left arms at Baseline, Week 4, Week 12, Week 24, Week 36, Week 48 and Safety Follow-up.

The absolute total RWS surface envelope area (m^2) as well as areas for each of the quadrants will be calculated and provided by a vendor in a blinded fashion, with no access to treatment assignment information. The reachable workspace relative surface area (RSA) represents the portion of the unit hemisphere that is covered by an individual's hand movement.

For each treatment, descriptive statistics of RSA results per visit as well as the change from baseline will be presented by quadrant, for total upper quadrants (Q1+Q3) and total area (Q1+Q2+Q3+Q4) for the assessment with weights and without weights, and by dominant and non-dominant arm. An MMRM model will be used to analyze the change from baseline in total area with repeat number category, treatment group, visit, and treatment-by-visit interactions as fixed effects and baseline value of the total area as a covariate. A separate model will be run with and without weights and for the dominant and non-dominant hand. Within-group LS mean changes from baseline, the associated SEs and 2-sided 95% CIs, treatment differences in LS mean changes from baseline at post-baseline visits and the associated 2-sided 95% CIs and 2-sided p-values will be derived from the MMRM model and will be provided in the summary table. An unstructured covariance matrix will be used to model the correlation among repeated measurements within each subject. If models using unstructured covariance do not converge, an AR(1) covariance structured will be used instead. Similar methods will be used to analyze the change from baseline in RSA for each quadrant.

Summary tables will be generated, showing percentage of subjects with RWS decline of $\geq 5\%$, $\geq 2\%$ at each post-baseline timepoint.

See [Section 4.6, #6](#) and [#7](#), for sub-group analyses to be conducted on this endpoint.

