5.3. MSK MRI Muscle Fat Fraction, Lean Muscle Volume and Muscle Fat Infiltration

The cross-sectional composite scores will be used to correlate the results with Clinical Outcome Assessments (i.e. TUG and RWS). Only summary statistics will be presented for these parameters.

The cross-sectional results will be further presented by extremity i.e. upper extremity, lower extremity, and total results. The convention that will be used to get extremity equivalent of the cross-sectional results is provided in Table 5-3.

Table 5-3. Extremity Equivalent of MRI Cross-sectional Results.

MRI Cross-sectional Results	Equivalent Extremity
FSHD TUG Cross-sectional	Lower extremity (LE)
RWS Right Cross-sectional	Right upper extremity (RUE)
RWS Left Cross-sectional	Left upper extremity (LUE)
RUE + LUE	Upper extremity (UE)
LE + RUE + LUE	Total

In addition, Spearman correlation coefficients will be used to assess relationships between the by extremity MRI results and classical and FSHD TUG and RWS results by visit. The Spearman correlation coefficient and p-value will be calculated within each treatment and presented in a table. This will also be graphically presented using scatterplots. Specifically, the following relationships will be assessed:

- LE vs. FSHD-TUG
- LE vs. Classical TUG
- RUE vs. RWS
- LUE vs. RWS
- UE vs. RWS

- TOTAL vs. FSHD-TUG
- TOTAL vs. Classical TUG
- TOTAL vs. RWS

The longitudinal composite scores are used to measure the change from baseline at each post-baseline visit. This is the result that will be used in the MMRM model.

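### The MRI–function correlations are planned only within treatment arm; at the pre-treatment visit a single all-subject coefficient would be more precise at no cost

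*SAP*

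**What the plan says.** Section 5.3 of the SAP Addendum sets out the analysis: "Spearman correlation coefficients will be used to assess relationships between the by extremity MRI results and classical and FSHD TUG and RWS results by visit". It then fixes the grouping: "The Spearman correlation coefficient and p-value will be calculated within each treatment and presented in a table". Scatterplots are planned as well. Neither a pooled nor an arm-adjusted coefficient is specified at any visit, and no confidence interval is requested.

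On timing, SAP Section 8.3 says of the MRI: "This will be assessed at Screening, Week 12, and Week 48". SAP Sections 8.4.1 and 8.4.2 start RWS and TUG at baseline. SAP Appendix 15.6 describes the cross-sectional composites as whole-body measures of how far the disease has affected muscle, to be correlated with severity or functional scores. The Addendum keeps them apart from the longitudinal composites, which go into the repeated-measures model.

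On side, Table 5-3 of the Addendum derives the right upper extremity result (RUE) from "RWS Right Cross-sectional" and the left one (LUE) from the matching left-sided entry. The functional partner in each upper-extremity pair is given only as RWS. SAP Section 8.4.1 says of RWS: "The evaluation will be performed with and without weights and on both the right and left arms at Baseline". It then summarises the results by quadrant, upper quadrants and total area, with and without weights, "and by dominant and non-dominant arm".

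**The concern.** Whether MRI findings track function before treatment is a question about FSHD, so the whole cohort is the natural sample. Allocation is 1:1 at Day 1, so any baseline difference between arms in this correlation is chance. Two half-size coefficients, each with its own p-value, describe a moderate association less sharply than one. They also invite a reader to conclude that MRI tracks function in one arm but not in the other.

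A smaller matter is that the RWS variable in each pair is not fully named. RWS exists for two arms, two weight conditions and several areas, and its main summaries use dominant and non-dominant arm while the MRI composites are right and left. The Protocol notes in Section 1.1 that "Asymmetry of muscle involvement is common", so the side is worth stating.

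**Working it through.** **The plan's own figure.** The documents give no power or precision for the correlations. The only sample-size statement is for the primary endpoint: effect size 0.70, 80% power, two-sided 0.05, 34 per group, 68 in total, about 76 randomised. The noncentral t gives power 0.7997 at 33 per group and 0.8116 at 34, so 34 is right. Allowing for 10% non-evaluable, 68 / 0.90 = 75.6, which rounds up to 76. The stated figures reproduce.

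**Inputs for the correlations.**
- 80 subjects enrolled (Protocol Section 3.1.1).
- 1:1 allocation (Protocol Section 5.1). About 40 per arm is an assumption, because exact arm sizes are not given.
- Two-sided 0.05.
- The true correlation is not in the documents. Values of 0.3, 0.5 and 0.7 are assumed to show the range.

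**Formulas** (Fisher z with the usual Spearman variance factor).
- SE = √(1.06 / (n − 3))
- 95% CI = tanh(atanh ρ ± 1.96 × SE)
- Power ≈ Φ(atanh ρ / SE − 1.96)
- Correlation detectable with 80% power = tanh((1.96 + 0.842) × SE)

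**Standard errors.** One arm: √(1.06/37) = 0.169. Pooled: √(1.06/77) = 0.117. The ratio is √(77/37) = 1.44, so a one-arm interval is 1.44 times as wide on the z scale.

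**Worked case, ρ = 0.3.** atanh 0.3 = 0.3095. One arm: 0.3095/0.1693 − 1.96 = −0.13, power 45%. Pooled: 0.3095/0.1173 − 1.96 = 0.68, power 75%.

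| Assumed ρ | 95% CI, n = 40 | 95% CI, n = 80 | Power, n = 40 | Power, n = 80 |
|---|---|---|---|---|
| 0.3 | −0.02 to 0.57 | 0.08 to 0.49 | 45% | 75% |
| 0.5 | 0.21 to 0.71 | 0.31 to 0.65 | 90% | 99.7% |
| 0.7 | 0.49 to 0.83 | 0.56 to 0.80 | 99.9% | about 100% |

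The correlation detectable with 80% power is about 0.44 in one arm and 0.32 pooled. If only 34 per arm (68 pooled) have usable pairs, these become 0.48 and 0.34, and power at ρ = 0.3 becomes 39% and 68%.

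**Chance disagreement between arms.** If both arms share the same true correlation, the probability that exactly one reaches p < 0.05 is 2 × power × (1 − power). At ρ = 0.3 this is 2 × 0.45 × 0.55, about one half. At ρ = 0.5 it is 2 × 0.90 × 0.10 = 18%.

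**Recoverable information.** Averaging the two arm-specific Fisher z values gives SE = √(1.06 / (2 × 37)) = 0.120, against 0.117 pooled. The plan does not call for this step.

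**The case against.** The strongest reply is that this is a matter of display. SAP Section 4.1 makes presentation by treatment group the default, so the by-arm table follows a stated convention. All subjects are still analysed, and a reader can combine the two coefficients with almost no loss (0.120 against 0.117). That stands: one might infer that half the data are thrown away, and they are not. What remains is that the planned table shows two imprecise coefficients with separate p-values and leaves the combining to the reader. Section 4.1 itself adds a total column for baseline tables, so an all-subject baseline result has precedent.

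A second reply is that baseline is never named. That is true. It is inferred from the by-visit wording and the assessment schedule, and nothing excludes it.

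A third is that by-arm results after baseline are sensible, because treatment could change the relation between imaging and function. That also stands. An arm-adjusted overall coefficient at Weeks 12 and 48 would be a preference. At Week 48 it would also be hard to interpret, since 12 subjects moved to open-label losmapimod at Week 24 and are analysed as randomised.

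Fourth, correlations of 0.3 are assumed and sit where splitting costs most. At 0.5 each arm already has about 90% power, and the gain from pooling is mainly a narrower interval.

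On side, a reader might infer that right-arm MRI will be set against left-arm reach in left-handed subjects. The documents do not support that. Table 5-3 labels the composites right and left, RWS is measured on both arms, and nothing says the dominant and non-dominant results feed these pairs. The definitions that follow in Appendix 15.6 are not visible in the text available for this review and may settle it.

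**Conclusion.** The point holds for the pre-treatment visit and is of low severity. With about 40 per arm instead of about 80 pooled, intervals are 1.44 times as wide on the z scale, and power falls from 75% to 45% at an assumed correlation of 0.3 and from over 99% to about 90% at 0.5. This rests on roughly equal arms, near-complete baseline pairs and assumed correlations.

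It may be tempting to read this as undermining the LMV key endpoint. It does not. That test uses change in the longitudinal composite, whereas these correlations use the cross-sectional scores, are exploratory and lie outside the testing hierarchy of SAP Section 8.1. No test or decision in the trial changes. The RWS side, weight condition and area are missing detail, and no wrong pairing has been shown.

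**What to change.** In Addendum Section 5.3, state that at baseline (screening MRI with baseline TUG and RWS) the Spearman coefficient and its 95% confidence interval will be reported for all subjects combined as the main result. Keep the by-arm values at Weeks 12 and 48.

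As a clarification, state that RUE is paired with right-arm RWS and LUE with left-arm RWS. Name the weight condition and the area used (total or a given quadrant). For the pairs that use both arms together, say how the two RWS results are combined.

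The cost is one added baseline result per pair in a planned table and a few lines of text. No new data are needed.

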5.4. Reachable Work Space With and Without Weights

The % change/year in RSA will be analyzed. A linear mixed-effects model will be used to analyze the total RSA, with treatment group as a fixed effect, and intercept, time and treatment-by-time interaction as random effects, and with adjustment for repeat number category and region (EU, USA, and Canada). Within-group LS mean of slope and the associated SEs, intercept and the associated SE, differences in the LS mean of slope and the associated 2-sided 95% CIs and 2-sided p-values will be derived from the linear mixed-model and will be provided in the summary table. In addition, the % change/year will be presented and will be derived as $[(\text{slope} * 365) / \text{baseline}] * 100$ where baseline is the LS mean of the intercept. Difference in % change/year between treatments will also be presented.

A separate model will be run with and without weights and for the dominant and non-dominant hand. An unstructured covariance matrix will be used to model the correlation among repeated measurements within each subject. Similar methods will be used to analyze the change from baseline in RSA for each quadrant.

The analysis related to functional work space (FWS) will no longer be done. According to the vendor, majority of the sessions were collected on normal speed and the table on FWS to show subjects belonging to normal or low speed will not give much information. In addition, the listing to show the detected will also be removed since this data was removed by the vendor.

[figure not shown]

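### The reachable work space slope model puts time and treatment-by-time only in the random part, so it cannot estimate or test the mean slopes it is meant to report

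*SAP*

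**What the plan says.** Addendum section 5.4 models total relative surface area (RSA) with a linear mixed model "with treatment group as a fixed effect, and intercept, time and treatment-by-time interaction as random effects". It adjusts for repeat number category and region, neither of which involves time.

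From that model it requires "Within-group LS mean of slope and the associated SEs, intercept and the associated SE, differences in the LS mean of slope", and states that "2-sided p-values will be derived from the linear mixed-model". The percentage change per year is the slope times 365, divided by baseline, times 100, "where baseline is the LS mean of the intercept". A further sentence says "An unstructured covariance matrix will be used to model the correlation among repeated measurements within each subject". The model is run separately with and without weights and for the dominant and non-dominant hand, and similar methods are to be used for each quadrant.

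The RWS repeated-measures model in SAP 8.4.1 is written differently, "with repeat number category, treatment group, visit, and treatment-by-visit interactions as fixed effects". The FSHD TUG and PGIC models in addendum 5.5 and 5.6 also list visit and treatment-by-visit as fixed. Nothing in the protocol, SAP or addendum adds fixed time terms to the slope model.

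**The concern.** A random effect describes how subjects scatter around a mean; it does not supply the mean. If time and treatment-by-time appear only as random effects, the mean slope is set to zero in both arms and the fixed part can express only a constant difference in level. There is then no LS mean slope, no slope difference, and nothing to attach a standard error or p-value to.

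The random treatment-by-time term does not help. Treatment is constant within a subject, so the term can let slope variance differ between arms but cannot carry a difference in mean slope.

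The annual rate of change by arm is the whole purpose of this added analysis, and the repeated-measures model does not report it. Whoever programs the table must either depart from the written model without a pre-specified rule, or build slopes from predicted random effects. The second route attenuates the difference and moves part of it into the treatment main effect.

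**Working it through.** The documents give no sample size, power or effect size for the RWS slopes, so there is no stated figure to reproduce. The main check uses only the model's structure.

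**1. Fixed part**

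| Model | Fixed-effect columns |
|---|---|
| As written | intercept, region (2 columns), treatment, repeat category |
| With time terms fixed | the same, plus time and treatment × time |

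As written, E[RSA] = intercept + region + treatment + repeat category. Its derivative with respect to time is 0 in each arm. Mean slope, slope difference and percentage change per year are all 0 by construction, with no standard error.

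**2. Random part**

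Each subject's random-effects matrix has columns 1, t and treatment × t. On placebo the third column is zero; on losmapimod it equals the second. The rank is 2 of 3 in both arms, so the separate time and treatment-by-time effects of one subject cannot be distinguished.

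**3. Where the unmodelled slope goes**

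It inflates the slope variance. In large samples with equal arms, fitted slope variance = true slope variance + average over arms of (mean slope)². With an assumed true slope SD of 0.02 per year:

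- Both arms at −0.04: √(0.02² + 0.04²) = √0.0020 = 0.045.
- Arms at −0.04 and 0: √(0.02² + 0.04²/2) = √0.0012 = 0.035.

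A simulation of 100 trials per case gave 0.044 and 0.034. It took 80 subjects from SAP 3.1 and baseline plus Weeks 4, 12, 24, 36 and 48 from SAP 3.2.3; it assumed intercept SD 0.12 and residual SD 0.03. It used a random intercept and slope, without the redundant third term.

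With fixed time terms, the same data gave:

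- Slope SD 0.018 and placebo slope −0.0396.
- Slope difference −0.00004 when the truth was 0, and 0.0400 when it was 0.04.
- p < 0.05 for treatment-by-time in 8 of 100 null trials. The Monte Carlo standard error at 5% is √(0.05 × 0.95/100) = 0.022, so this is compatible with 5%.
- p < 0.05 in 97 of 100 trials with a true difference of 0.04.

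**4. Size of the error if predicted slopes are averaged**

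Assumptions: 40 per arm, the same visits, mean RSA 0.70, between-subject SD 0.12, and true slopes of −0.04 and 0 per year, so a true difference of 0.04. There were 80 simulated trials per setting.

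| Slope SD | Residual SD | Fixed time terms | As written, predicted slopes averaged | Shortfall against 0.04 |
|---|---|---|---|---|
| 0.03 | 0.03 | 0.039–0.040 | 0.021 | 1 − 0.021/0.04 = 48% |
| 0.05 | 0.03 | 0.039–0.040 | 0.027 | 1 − 0.027/0.04 = 33% |
| 0.03 | 0.05 | 0.039–0.040 | 0.012 | 1 − 0.012/0.04 = 70% |

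A large-sample calculation under the same assumptions gives 0.022, 0.028 and 0.012. It finds the limiting fit of the as-written model and averages the predicted slopes, the slope element of GZ′V⁻¹(y − fitted mean), within each arm. Against a baseline of 0.70, the true difference is 0.04/0.70 = 5.7 percentage points per year. The averaged predictions would report 0.021/0.70 = 3.0, 0.027/0.70 = 3.9 or 0.012/0.70 = 1.7.

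**The case against.** The strongest reply is that this is a slip of wording. LS means, standard errors and p-values for slopes are fixed-effect outputs, so the required table can be produced only by fitting time and treatment-by-time as fixed. A standard random-coefficients model was probably intended, and a programmer would probably fit it. The addendum never asks for averaged predicted slopes, so the attenuation above describes one possible misimplementation, under variances that are not in the documents.

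Much of that is fair. The attenuation should not be read as the expected bias of this trial. It is also true that the variance of a random treatment-by-time effect can be estimated across arms, for example with a diagonal covariance matrix, even though the individual effects cannot be separated.

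The stakes are limited too. RWS is exploratory, and protocol 7.6.4 gives such comparisons no confirmatory value. It lies outside the DUX4, LMV and FSHD TUG hierarchy of SAP 8.1. The model in SAP 8.4.1 compares the arms validly at each visit.

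What remains is that the text separates fixed from random terms explicitly and puts the time terms on the wrong side, while neighbouring models put theirs on the right side. A reader has to infer a different model from the requested outputs. The objection bears on importance, not on whether the sentence is wrong.

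**Conclusion.** The concern holds. As written, the model in addendum 5.4 has no parameter for the mean slope in either arm or for the slope difference, so it cannot deliver the estimate, interval, p-value or percentage change per year that the section demands. This follows from the fixed-effect columns and rests on no assumed number.

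The understatement of roughly 30% to 70% applies only if predicted subject slopes are averaged, and only under the assumed slopes and variances. The defect runs through the weight, hand and quadrant versions of the model. It should be corrected before the analysis is run, but it does not touch any primary, secondary or key endpoint.

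**What to change.** Replace the model sentence in addendum 5.4 with one that specifies:

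- fixed effects for treatment group, time (continuous, in days, to match the factor of 365), treatment-by-time, repeat number category and region;
- a random intercept and random time slope for each subject, with an unstructured 2 × 2 covariance matrix for these two effects;
- the fixed treatment-by-time coefficient as the slope difference, with its 95% CI and p-value.

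Apply the same specification to the weight, hand and quadrant models. Two details should be settled in the same edit:

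- **Convergence.** Unlike SAP 8.4.1 and addendum 5.5, this section gives no fallback if the unstructured fit fails. Uncorrelated random intercept and slope would serve.
- **Quadrant response.** The section refers to change from baseline for the quadrants but to RSA itself for the total. RSA level should be used throughout, because a change score is zero at baseline and its intercept cannot sensibly be the denominator for percentage change.

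The cost is a short text edit. It needs no new data and leaves the other analyses as they are.

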5.5. FSHD TUG

An MMRM model will also be used to analyze the change from baseline in the sum of the 3 FSHD TUG segments average completion time with repeat number category, treatment group, visit, and treatment-by-visit interaction as fixed effects and baseline value as a covariate. Within-group LS mean changes from baseline, the associated SEs and 2-sided 95% CIs, treatment differences in LS mean changes from baseline at post-baseline visits and the associated 2-sided 95% CIs and 2-sided p-values will be derived from the MMRM model and will be provided in the summary table. An unstructured covariance matrix will be used to model the correlation among repeated measurements within each subject. If models using unstructured covariance do not converge, an AR(1) covariance structure will be used instead.

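### The addendum's RWS slope model is mis-specified: its covariance is over-parameterised with no stated way out, and the slope difference is not a parameter of the model as written.

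*SAP*

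**What the plan says.** Addendum 5.4 models total relative surface area (RSA) "with treatment group as a fixed effect, and intercept, time and treatment-by-time interaction as random effects", adjusting for repeat number category and region. On covariance it says only this, at the point where it splits the fits by "dominant and non-dominant hand. An unstructured covariance matrix will be used to model the correlation among repeated measurements within each subject". It gives no alternative if the fit fails.

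The required output is within-group mean slopes, and "differences in the LS mean of slope and the associated 2-sided 95% CIs and 2-sided p-values will be derived from the linear mixed-model". Separate models are run with and without weights and for each hand. Quadrants are to be analysed by similar methods.

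Two neighbouring texts use the same unstructured-matrix sentence for mixed models for repeated measures (MMRMs) and do give an alternative. SAP 8.4.1, for RWS change from baseline, continues: "If models using unstructured covariance do not converge, an AR(1) covariance structured will be used instead". Addendum 5.5, for the FSHD TUG, has: "If models using unstructured covariance do not converge, an AR(1) covariance structure will be used instead". Addendum 5.6 repeats that rule for the PGIC.

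**The concern.** An unstructured matrix over visits suits an MMRM, where it is the only description of within-subject correlation. Addendum 5.4 puts the same sentence into a random-coefficient model, where the random effects already describe that correlation. Read literally, the two parts compete. If the sentence instead describes the matrix of the listed random effects, there is a different problem: treatment does not vary within a subject, so a random treatment-by-time effect cannot be told apart from a random time effect.

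The mean part is also incomplete. Random effects have mean zero. With time and treatment-by-time listed only as random, no parameter represents the average slope in either arm or the difference between arms, which is what the analysis is meant to test.

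At stake is reproducibility. A programmer who follows the text may get a singular solution and must then choose another structure, possibly after seeing the data. That choice sets the standard error and p-value of the slope difference.

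**Working it through.** The documents state no figure for this model, so there is none to reproduce. The check counts covariance parameters and asks how many the data can determine.

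**Inputs**
- Visits (SAP 8.4.1): RWS is assessed "on both the right and left arms at Baseline, Week 4, Week 12, Week 24, Week 36, Week 48 and Safety Follow-up". The count uses the six scheduled visits, baseline to Week 48.
- Random effects (Addendum 5.4): "intercept, time and treatment-by-time interaction as random effects", so three per subject.
- Treatment (SAP 4.8): 1:1 parallel arms, constant within a subject for the randomised comparison.

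**Formula.** The marginal covariance in each arm is V = ZGZ' + R. Here G is the random-effects matrix, R the residual matrix, and Z has columns for intercept, time and treatment x time. The third column is zero on placebo and equals time on losmapimod. Write g11, g12, g13, g22, g23, g33 for the six entries of G.

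**Unstructured 3x3 G, independent residuals**
- Parameters: 6 + 1 = 7.
- Placebo identifies g11, g12, g22 and the residual variance: 4.
- Losmapimod adds the intercept-slope covariance g12 + g13 and the slope variance g22 + 2*g23 + g33: 2 more.
- Identifiable: 4 + 2 = 6. Only the sum 2*g23 + g33 is determined, not its two parts. Varying the visit days does not help.

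**The same G plus an unstructured 6x6 R**
- Parameters: 6 + (6 x 7)/2 = 6 + 21 = 27.
- At nominal visits, the placebo matrix has 21 free entries and R fills all of them. The losmapimod arm adds the same 2 quantities. Identifiable: 21 + 2 = 23.
- With days varied inside the protocol windows: 25. The two still missing are the split of g11 from R and the split of g23 from g33.
- Dropping random treatment-by-time but keeping unstructured R: 3 + 21 = 24 parameters, 21 identifiable at nominal visits and 23 with varying days.

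**Random intercept and time, unstructured 2x2 G, independent residuals**
- Parameters: 3 + 1 = 4, all identifiable.

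The numerical rank of the map from parameters to the two V matrices agrees with each count. These counts do not depend on any assumed variance.

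**Does the slope contrast suffer?** Once time and treatment-by-time are in the fixed part, the contrast and its standard error depend on V alone. Moving along the unidentified directions left the standard error unchanged: 0.01583 in four splits of g23 and g33, and 0.01551 in three splits between G and R.

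**Does a literal fit run?** In 100 simulated trials (80 subjects, assumed variances, fixed time and treatment-by-time, independent residuals, Python statsmodels):
- The 2x2 model gave a usable fit in 100.
- The 3x3 model gave a finite standard error in 58, stopped with a singular matrix in 41 and returned a missing standard error in 1.
- Where both fitted, slope-difference estimates agreed to about 1e-14 and standard errors to within 3%.

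**Does the choice of resolution matter?** Unstructured R alone and 2x2 G with independent residuals imply different V matrices. In an illustrative simulation (80 subjects, assumed variances, Wald tests, 60 trials per scenario), the median ratio of the first standard error to the second was 0.95 to 0.98. The two disagreed on p<0.05 in 5 of 60 trials with independent residuals and 7 of 60 with serially correlated residuals.

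**The case against.** A reader might infer that the slope comparison cannot be fitted at all. The documents do not support that. The marginal covariance is identified, the standard error of the contrast does not depend on the unidentified split, and over-parameterised fits sometimes run. The failures above came from statsmodels, whereas the SAP specifies SAS, which may behave differently.

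A reader might also infer that every reading is unidentifiable. Because 5.4 asks for mean slopes, an experienced programmer would probably fit fixed time and treatment-by-time with a 2x2 intercept-slope matrix, and that model is identifiable. It is nevertheless a departure from the text, which places treatment-by-time among the random effects and ties the unstructured matrix to the repeated measurements.

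Nor was the AR(1) fallback dropped. The rule in SAP 8.4.1 belongs to the change-from-baseline MMRM, which 5.4 does not withdraw. It would not cure the problem either: AR(1) residuals with the 3x3 G give 6 + 2 = 8 parameters, of which 7 are identifiable.

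Finally, RWS is exploratory (SAP 3.2.3) and outside the testing hierarchy (SAP 8.1). Protocol 7.6.4 gives exploratory comparisons no confirmatory value. That objection stands and limits the severity. It does not make the specification correct.

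**Conclusion.** Wrong as written, with modest severity. Addendum 5.4 states a covariance that the design cannot identify in full: 6 of 7 parameters with the 3x3 G, and 23 of 27 (25 with varying days) with unstructured R added. It also omits the fixed terms that define the slopes it wants compared, and gives no rule for resolving either problem. A literal fit may fail, and the covariance model behind the slope p-value could then be chosen after the data are seen. The slope contrast is estimable once its fixed terms are present.

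At least 2 weight conditions x 2 hands = 4 fits are affected. If the quadrants use the slope model too, it is 4 x (1 total + 4 quadrants) = 20. The text leaves this open, because it describes the quadrant analysis as change from baseline.

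The parameter counts rest only on the visit schedule and parallel arms. The failure rates and standard-error comparisons rest on assumed variances, since the documents give none for RSA.

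**What to change.** Replace the model and covariance sentences in Addendum 5.4 with:

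*Fixed effects: treatment, time, treatment-by-time, repeat number category and region. Random effects: subject intercept and time, with an unstructured 2x2 covariance; residuals independent with common variance; no random treatment-by-time and no unstructured residual matrix. If this does not converge, the intercept-slope covariance is set to zero. Kenward-Roger degrees of freedom.*

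The fixed terms must go in together with the removal of random treatment-by-time. Otherwise the model has no treatment-by-time term at all. Kenward-Roger needs naming here because Addendum 5.1 states it under the MMRM heading. The wording assumes the same 2x2 matrix in both arms. Section 5.4 should also say whether the quadrants use this model or the change-from-baseline MMRM.

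The cost is a few sentences, with no extra data and no added programming burden.
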